### **G4 Missing Outcome Data**

Missing data and patterns will be assessed monthly by the data manager. Remedial measures, including retraining of staff, will be used as needed to minimize missing data.

We plan for an intent to treat analysis. In doing this, study participants that are lost to followup will be presumed to not have an acute urinary tract infection from the time of last contact with the study participant.

We will additionally have a per protocol analysis.

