## 2.h When and How to Withdraw Subjects

Withdrawal of subject as the result of subject decision:

- A subject enrolled in the study may decide to withdraw from the research at any time by notifying the principle investigator and/or another member of the research team by calling the office at [contact] and letting the office staff know she needs to speak to the principle investigator and/or member of the research team. The investigator speaking with the subject will clarify whether the subject wishes to withdraw from all components of the trial or only from a particular component of the trial. If the latter is desired, then follow-up data collection activities, for which the subject previously gave consent may continue.
- If a subject withdraws from the study then a member of the research team will ask the subject if she is willing to complete an study exit survey and/or the information that would have been gathered at the originally planned 3 month follow up appointment. This exit survey and 3 month follow up visit information may be obtained by appointment, by phone, or by mail.

Withdrawal of subject as the result of investigator decision:

- If an investigator terminates a subject's participation in the trial, the investigator should explain to the subject the reasons for this action and, as appropriate, other treatment options.
- If subjects were to have a serious adverse reaction to the medication, the investigator would recommend discontinuation of medication.

---

- An investigator may terminate a subject's participation in the study to protect a participant from excessive risk or risk with demonstrated lack of benefits or to maintain integrity of the data (for instance if a participant is not following study procedures or may be deliberately providing false information).
- If a subject is treated for an acute UTI during the 90 day study period without having an urine culture performed then data will be assessed both as if she did and did not have an acute UTI. She does not need to be withdrawn from the study as of the date of treatment of subjective UTI.. Antibiotics used for reasons other than UTI do not require subject withdrawal. Data obtained for any subject to the point of study withdrawal may be used in the study.

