- If a subject is withdrawn from the study then a member of the research team will ask the subject if she is willing to complete an study exit survey and/or the information that would have been gathered at the originally planned 3 month follow up appointment. This exit survey and 3 month follow up visit information may be obtained by appointment, by phone, or by mail.
- Subjects lost to follow up will be presumed to not have an acute urinary tract infection from the time of last contact.

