### 3.g Blinding of Study Drug

For the treatment arm of the RCT, the D-mannose powder will be ordered and distributed by the research team. The manufacturer label will be covered up/removed and a study label stating contents of a nutraceutical will be used to maintain patient blinding to which nutraceutical is being used. The research team will not be blinded to the study drug. There are no placebos being used in this study.

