## **G   Statistical Plan**

### ***G1   Sample Size Determination and Power***

We based our sample size estimate on assumptions for our primary aim, as this is the most important aim for providing information to support future recommendations and studies aimed at individualized patient care. The first published study on D-mannose was a RCT that showed 14.6% of rUTI patients develop another UTI while on treatment [9]. To be conservative in our sample size calculations, we assume 20% of patient on D-mannose will develop a UTI during the three-month treatment period. Very few studies have stated the percent of rUTI patients that develop another UTI while on vaginal estrogen therapy [27-29]. Due to the range of the published values, an average of these numbers was taken to arrive at an assumption that 45% of patients on only vaginal estrogen therapy will develop another UTI during the treatment period. We also accounted for a 10% dropout rate during the study period. Using these numbers to determine sample size, we calculated 60 patients would be needed per RCT arm for a total of 120 patients in the RCT. We recognize that our power for secondary aims is lower; however, we included these to begin to explore these other areas that are fundamental for understanding the underlying mechanism of D-mannose and how it works with rUTI. We have decided to also enroll 60 patients in the Observational arm of the study.

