### **G3 Analysis Plan and Statistical Methods**

We are studying D-mannose in postmenopausal women with a history of rUTI on VET. We will plan for an intent to treat analysis with an additional per protocol analysis likely.

For our primary outcome of the RCT, we will calculate the cumulative incidence of symptomatic culture-proven UTIs. If we have loss to follow-up, we will use the Kaplan-Meier method to calculate the cumulative incidence by arm (i.e., 1.0 - survival). We will compare the cumulative incidence between arms by chi-squared tests, Fisher's exact tests, or log-rank tests, as appropriate. Although women will be randomized into the two arms, we will compare their distributions of potential confounding variables by calculating group-specific means and proportions, as appropriate. If these differ by an appreciable degree, we will calculate adjusted associations, using logistic or Cox proportional hazards regression, as appropriate.

We will calculate the incidence of side effects and discontinuation as the number of women in the D-mannose +VET arm who experience these events during follow-up divided by the number of women in the D-mannose +VET arm. 95% confidence limits will be calculated by normal approximation or the Clopper-Pearson exact method, as appropriate.

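### Two incompatible rules for women lost to follow-up: section G3 implies censoring them, sections G4 and 2.h count them as UTI-free, and nothing says which is primary

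*Combined protocol and SAP*

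**What the plan says.** Section G3 makes the cumulative incidence of symptomatic, culture-proven UTI the primary outcome of the RCT and adds: "If we have loss to follow-up, we will use the Kaplan-Meier method to calculate the cumulative incidence by arm". It then leaves the test open among chi-squared, Fisher's exact and log-rank.

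Section G4 plans an intent-to-treat analysis and says that, in doing so, participants "lost to followup will be presumed to not have an acute urinary tract infection from the time of last contact". Section 2.h has the same rule: "Subjects lost to follow up will be presumed to not have an acute urinary tract infection from the time of last contact".

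For women who withdraw or are withdrawn, section 2.h says only: "Data obtained for any subject to the point of study withdrawal may be used in the study". It does not say whether they are then censored or presumed UTI-free. The one two-way analysis in the plan concerns a woman treated for a UTI without a culture, for whom "data will be assessed both as if she did and did not have an acute UTI". It does not cover loss to follow-up. The per-protocol analysis in G4 is not described as addressing loss either.

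**The concern.** Take a woman last contacted on day 30 with no UTI so far. Under G3 she leaves the risk set on day 30 and contributes nothing afterwards. Under G4 and 2.h she stays in the denominator to day 90 as a woman without a UTI. If every lost woman is carried forward in this way, one minus the Kaplan-Meier estimate equals the simple proportion, and the Kaplan-Meier clause in G3 has no purpose. The two rules agree only if nobody is lost or no lost woman has a later UTI.

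The open choice of test does not settle the matter. Log-rank goes with censoring; chi-squared and Fisher's exact go with an imputed proportion. Two analysts following the plan could therefore report different primary incidences and p-values from the same data. The interim efficacy look in section G2 has the same ambiguity.

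Intent to treat does not require the presumption. It fixes the arm in which a woman is analysed; it does not supply an outcome that nobody observed. Nor is the presumption reliably conservative, because it flatters whichever arm loses more women. Unequal loss is possible, since section 3.g states: "There are no placebos being used in this study".

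**Working it through.** **Inputs from section G1.** "we assume 20% of patient on D-mannose will develop a UTI during the three-month treatment period"; "45% of patients on only vaginal estrogen therapy will develop another UTI during the treatment period"; 10% dropout; 60 women per arm. Follow-up is 90 days (section E1).

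**Assumptions not in the documents.** Two-sided alpha of 0.05 and 80% power; a constant UTI hazard; the same risk in lost and retained women; loss either uniform over the 90 days or entirely at the start; any split of loss by arm.

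**The plan's own figure.** Two proportions, pooled variance, no continuity correction:

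n = [1.96 × √(2 × 0.325 × 0.675) + 0.8416 × √(0.45 × 0.55 + 0.20 × 0.80)]² / 0.25² = 53.9, rounded up to 54 per arm. Then 54 / (1 − 0.10) = 60. The stated 60 per arm is reproduced.

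**Incidence reported under the G4 rule.** With true risk p and lost fraction d, the reported risk is (1 − d)p + dq. Here q is the chance that a lost woman had her UTI before last contact:
- loss at the start: q = 0;
- uniform loss: q = 1 − (1 − e^(−h))/h, with h = −ln(1 − p). This gives q = 0.247 for p = 0.45 and q = 0.104 for p = 0.20.

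Equal 10% loss:
- uniform: 0.9 × 0.45 + 0.1 × 0.247 = 43.0% and 0.9 × 0.20 + 0.1 × 0.104 = 19.0%; difference 23.9 points before rounding;
- at the start: 0.9 × 0.45 = 40.5% and 0.9 × 0.20 = 18.0%; difference 22.5 points.

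The true difference is 25 points. The risk ratio stays at 0.44 in both cases.

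**Power and type I error under the G4 rule.** Exact enumeration of two binomials, 60 per arm, uncorrected chi-squared; the null case has 45% in both arms. Each range runs from uniform loss to loss at the start, in whichever order is lower first.

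| Loss | Type I error | Power |
|---|---|---|
| None | 5.4% | 84.8% |
| 10% / 10% (planned total) | 5.1–5.3% | 79–83% |
| 12% / 8% (assumed) | at most 5.6% | not tabulated |
| 15% / 5% (assumed) | 5.9–8.1% | 66–78% if control loses more; 87–89% if D-mannose loses more |
| 20% / 5% (assumed) | 6.6–11.9% | 56–74% or 88–91% |

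At 15%/5% with no true effect, the rule creates a difference of 2.0 to 4.5 points (for loss at the start, 0.95 × 0.45 − 0.85 × 0.45 = 4.5 points).

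**Both rules under the same test.** Simulated log-rank, with loss unrelated to UTI risk:
- equal 10% loss: power is 81–83% with censoring and 79–83% with the presumption, so the rule itself costs at most about 2 points;
- 15%/5%: type I error is about 5.0–5.5% with censoring and about 5.5% to 8% with the presumption.

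With Fisher's exact test, the G4 rule moves type I error from 3.4% with complete data to 3.8–5.5% at 15%/5%.

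**Extreme assignments at 10% loss, all at the start.** If all lost D-mannose women have a UTI and no lost control does: 0.18 + 0.10 = 28.0% versus 40.5%, a difference of 12.5 points. The reverse: 18.0% versus 0.405 + 0.10 = 50.5%, a difference of 32.5 points. These bounds hold whichever rule is chosen; they show what the missing outcomes could do.

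**The case against.** The strongest reply is that the choice matters little at the only loss figure in the documents. With 10% lost equally, the risk ratio is unchanged, and most of the fall in power from 85% comes from losing women rather than from the rule. That is correct, and the like-for-like cost is at most about 2 points.

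The larger figures need both a marked imbalance between arms and loss concentrated at the start. The documents give no loss by arm. The weekly reminders, six-week call, chart review and phone or mail completion make loss at the start a bound rather than a likely case. That also stands, and the unequal-loss rows are hypothetical. These procedures reduce loss, but they supply no rule for a woman who is never reached again.

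Uncorrected chi-squared already has a size of 5.4% here, so its figures should not be set directly against log-rank. Under one test the pattern remains: type I error rises above that test's own baseline for all three tests named in G3.

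Kaplan-Meier is not free of bias either. If lost women have UTIs treated elsewhere more often than those who stay, it too understates incidence. Section 2.f recognises that some women may prefer outside care. This is a reason for sensitivity analyses, not for presuming no UTI.

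Finally, one sentence of precedence would remove the contradiction. That is so, but choosing the presumption would keep an imputation that is wrong whenever a lost woman has a later UTI.

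**Conclusion.** The concern holds. Sections G3 and G4 (with 2.h) prescribe incompatible handling of the same women in the primary analysis, without precedence, and with the test also left open. This must be resolved before analysis because the primary result is not uniquely defined; the case does not depend on demonstrated bias.

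If the presumption in G4 is used and lost women carry the same risk as others, incidence is understated in both arms. At equal 10% loss the difference shrinks from 25 points to between 22.5 and 23.9, while the risk ratio and type I error are essentially preserved. If loss differs by arm, the arm with more loss looks better, two-sided type I error rises, and power moves either way. The size of that effect rests on assumed splits.

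**What to change.** 1. Remove the UTI-free presumption as the primary rule from sections 2.h and G4.
2. Make the G3 method primary: Kaplan-Meier cumulative incidence of first symptomatic, culture-proven UTI at day 90, censored at last contact.
3. State whether women who withdraw or are withdrawn are handled in the same way.
4. Name one test in advance, for example log-rank. It compares whole curves, so state that the day-90 difference is the reported estimate beside it.
5. Keep the presumption of no UTI as a sensitivity analysis, together with all lost women counted as having a UTI and the two cases that assign opposite outcomes by arm. Report loss by arm, with its timing.

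The cost is revised wording and a few extra analysis runs. The sample size can stay: with 60 per arm and 10% non-informative loss, log-rank with censoring has 81–83% power under the plan's assumed risks. The price is a slightly wider interval and an explicit assumption of non-informative censoring, which the sensitivity analyses in point 5 probe.

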### **G5 Unblinding Procedures**

Every attempt will be made to ensure that the patients enrolled in the RCT under the knowledge that a nutraceutical is being studied will continue to be blinded to which nutraceutical is being studied. If a patient is in the treatment arm of the RCT, and they are unblinded then this will be documented and reported to the research team for recording purposes.

---

## **H Data Handling and Record Keeping**

### **H1 Confidentiality and Security**

Confidential and informed consent will occur in a private counseling room. Every precaution will be taken to ensure data confidentiality. Only research team members will have access to both the paper and electronic data. Subjects will be assigned a unique study ID that will be used on all case report forms and database reporting. The database that will be used is REDCap which is HIPPA compliant, encrypted, and password protected. Electronic data files will be accessible only on password protected computers. Any hard copies will be maintained in a locked cabinet in a locked office by a member of the research team. Data collection will occur on participants' private devices (and sent to a locked phone) and/or on paper and placed in a locked cabinet in a locked office by a member of the research team. For text messaging, we will be using a SMS service that does not collect PHI. There will be strict adherence to data management protocols.

---

## ***H2 Training***

All members of the research team will be educated on the study protocol at a division meeting or meeting set up for training purposes. All members of the research team will be able to ask questions at this education session and after the education session to ensure they are comfortable with all aspects of the study protocol. Members of the research staff that will be using REDCap (Research Electronic Data Capture) will be trained on how to use this database.

## ***H3 Records Retention***

Subjects will be assigned a unique study ID that will be used on all case report forms and database reporting.

Any hard copies will be maintained in a locked cabinet in a locked office by a member of the research team.

Weekly study diary reminder response will be collected via text message. Data will be stored in REDCap which is HIPPA compliant, encrypted, and password protected. Work will only be done on password protected computers. Only members of the research team will have study information access.

---

## ***I Study Administration***

### ***I1 Organization and Participating Centers***

The location of this study will be the four outpatient office locations of the Division of Female Pelvic Medicine and Reconstructive Surgery in the Department of Obstetrics and Gynecology at Washington University in St. Louis School of Medicine.

### ***I2 Funding Source and Conflicts of Interest***

Funding for this project will be supplied by the division of Female Pelvic Medicine and Reconstructive Surgery. This is a division of the Department of Obstetrics and Gynecology in the Washington University in St. Louis School of Medicine.

### ***I3 Subject Stipends or Payments***

Subjects will not be reimbursed for their participation in this research study. Patients in the treatment arm of the RCT portion of the study will received their D-mannose as part of the study.

### ***I4 Study Timetable***

Study Measure (mo = months) [Month 0 = January 2018]	0-4 mo	4-8 mo	8-12 mo	12-16 mo	16-20 mo	20-24 mo
Patient enrollment						
3 mo of D-mannose treatment vs control treatment with patient follow up and re-examination						
Data analysis						
Manuscript preparation and submission						

## **J Publication Plan**

We plan use the data from this study to write a manuscript for publication in a respected peer-reviewed journal in a timely fashion. Journal choice will be dependent on study findings, but will likely be relating to the fields of female pelvic medicine and reconstructive surgery, gynecology, or urology.

## **K Attachments**

### **K1 Informed consent documents**

The following documents are attached in the myIRB application:

- Informed consent – RTC arm
- Informed consent – Observational arm

### **K2 Patient education brochures**

- Participant instructions – RCT arm
- Participant instructions – Observational arm

### **K3 Questionnaires or surveys**

The following documents are attached in the myIRB application:

- Nutraceutical efficacy in rUTI screening log
- Enrollment visit form – complete with participant
- Study Diary – RCT Arm
- Study Diary – Observational Arm
- Follow up call for Yes text response form
- 1 week confirmation of D-mannose in Observational Arm
- 6 week follow up phone call – RCT Arm
- 6 week follow up phone call – Observational Arm
- 3 month followup appointment form – RCT Arm
- 3 month followup appointment form – Observational Arm
- Exit survey (completed less than 90 days of study)
- Exit survey (completed 90 days of study)

